13.1 Sample size

Following Stage 1, we identified 5 different service models. On that basis, 15 examples of services in total will be included at Stage 2 – based on sample size calculations. To detect a standardised effect

size of 0.4 in a one-way ANOVA, with 90% power, a two-sided alpha of 0.05, and assuming five service model types identified in Stage 1, a total sample size of 120 children is required. Inflating this sample size for clustering of children within services, assuming an average number of 13 children recruited from each setting and an intra-cluster correlation coefficient (ICC) of 0.05, the required sample size increases to 195 children from 15 settings. This sample size does not currently account for loss to follow up, so we will allow up to 20% by extending our sample size to N=244 (recruiting approximately 15-16 individuals per service for 15 services). This ICC is likely conservative given the subjective nature of the outcome measures (Adams et al., 2004). In our statistical analysis, we will enhance power and precision by adjusting for individual and cluster level characteristics, including service type (which is by definition a cluster level characteristic) and corresponding baseline measures of the outcome variable.

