6.2 Risk assessment

This is a low-risk study. The research is purely observational, and no interventions will be implemented outside of the treatment as usual within services. Involvement in the study is entirely voluntary, and informed consent will be obtained prior to any data collection with participants. Participants will be asked questions about their/their child's wellbeing, mental health, health, quality of life, and experience of the service using measures that are routinely used in research with children and young people with learning disabilities.

We will complete a formal risk assessment before the study commences.

15 Site and Investigator selection

Each service, and each co-production case study will be a separate site, and a PI will be identified within each site. Identification of services is described in detail in Section 8 below. Identification of Co-Production Case Studies will be undertaken with the involvement of the family carer advisory group, professionals advisory group, and the SMG.

The study will be carried out at University of Warwick, under the supervision of the Chief Investigator ([name]). Fully trained Research Fellows and Research Assistants at the University of Warwick will be responsible for recruitment and all data collection. A Site Delegation Log and Roles and Responsibilities document will be completed and full contact details will be recorded for all Sites. A Site File, containing all relevant study documents will be prepared at the University of Warwick.

Once all study documentation is in place and a Site Initiation Visit has been completed, recruitment of services and participants into the study will begin.

Occasionally during the course of the study, amendments may be made to the study documentation, required approvals obtained, and the latest approved versions will be added to the Site File.

16 Selection of Services and Participants

All eligible services from Stage 1 of the MELD study will be considered (N=161), and sampling of services will be according to a systematic sampling process to select 15 Sites from the approximately 161 services included in Stage 1 (3 services per Class).

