It is inevitable that the referral of children to different service types will be a non-random process. Therefore, a crude comparison of outcomes of children in different service types will be prone to selection bias. To minimise this, the research team and stakeholders will construct a Directed Acyclic Graph (DAG) prior to data collection in Stage 2, which will outline our core assumptions around the causal pathways between service model (exposure) and child outcomes (Williams et al., 2018). This DAG will be used to identify key quantitative data to collect (e.g., confounders, mediators, and moderators) and will be used as an aid for modelling the relationship between service model and child outcomes. The final statistical models will depend on the DAG, but will broadly be a two-level linear regression model (children nested within services), with the child outcome measure at 12-months as the outcome, service model included as a fixed effect, and the corresponding child outcome collected at baseline also included as a covariate. Results will be reported as adjusted mean differences, 95% confidence intervals, and p-values. Mediation analyses will use the bootstrapped procedure as this method has no distributional assumptions on the indirect effect and is generally more robust (Bollen & Stine, 1990).

A detailed statistical analysis plan will be written and agreed by the study management team prior to any analysis taking place. A missing data strategy will be a part of the SAP. This is most likely to include an exploration of any setting/child determinants of missing outcome data (to infer likely missing mechanisms), and an analysis that is valid under a Missing At Random assumption (e.g. using maximum likelihood methods or multiple imputation).

When fitting models to describe the relationship between our service types and our outcome/s, we will adjust for confounding using multinomial propensity score weighting, as this approach tends to preserve the majority of a study sample and therefore maximises precision of estimates. When specifying our propensity score model, we will include outcome risk factors (informed by the DAG which defines the minimally required adjustment set) and exclude strong predictors of service model inclusion that are not associated with outcome. Following this, we will inspect the distribution of

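### The 90% power stated for Stage 2 does not follow from its calculation: with 15 services the five-model comparison has 10 denominator degrees of freedom, and unadjusted power is about 81%

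*Protocol*

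**What the plan says.** The Stage 2 protocol, section 13.1, sets a standardised effect "size of 0.4 in a one-way ANOVA, with 90% power, a two-sided alpha of 0.05" and continues "assuming five service model types identified in Stage 1, a total sample size of 120 children is required". It then assumes 13 children per setting and an ICC of 0.05, and concludes that "the required sample size increases to 195 children from 15 settings". Allowing for 20% loss to follow-up brings the total to 244.

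The number of services is fixed: "15 examples of services in total will be included at Stage 2". The Stage 2 section on selection of services and participants gives the split as "3 services per Class".

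Section 13.1 also says that power and precision will be improved by adjusting for individual and cluster characteristics, "including service type (which is by definition a cluster level characteristic"), and for the baseline value of the outcome. It gives no baseline correlation. It describes the ICC as probably conservative.

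Section 14 (Analysis, Stage 2) plans a "two-level linear regression model (children nested within services"), with service model as a fixed effect and the baseline outcome as a covariate. It adds multinomial propensity score weighting with sandwich variances. Neither section mentions between-service degrees of freedom or a small-cluster correction.

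**The concern.** All children in a service share one service model. Differences between models are therefore judged against variation between services within the same model, and only 15 services inform that. Multiplying the child count by a design effect enlarges the variance correctly, but the critical value of the F test still comes from about 190 denominator degrees of freedom when 10 are available. With few clusters per group this matters: the 5% critical value is 3.48 on (4, 10) degrees of freedom and 2.42 on (4, 190).

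Three smaller matters in the same paragraph make the figure hard to check:

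- The starting value of 120 does not come out of the stated inputs at alpha 0.05.
- The effect size of 0.4 is not named as Cohen's f.
- Service type, which is the exposure, is listed among the adjustments said to add power to its own comparison.

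The SAP supplied covers Stage 1 only and leaves Stage 2 to a separate SAP. Section 13.1 is therefore the only Stage 2 power statement in these documents, and it will be used to judge how informative the model comparison is.

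**Working it through.** **Inputs from the documents.** Five models, effect size 0.4, alpha 0.05, 90% power, 13 analysed children per service, 15 services, ICC 0.05 and 20% loss (Stage 2, section 13.1); three services per model (section on selection of services). Reading 0.4 as Cohen's f is an assumption, and the usual one for a one-way ANOVA.

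**1. Reproducing the plan's figures.** Balanced one-way ANOVA, noncentrality λ = N·f², degrees of freedom 4 and N − 5:

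| N | Power, alpha 0.05 | Power, alpha 0.025 |
|---|---|---|
| 100 | 89.6% | 83.3% |
| 102 | 90.3% | 84.3% |
| 105 | 91.2% | 85.6% |
| 115 | 93.8% | 89.4% |
| 120 | 94.8% | 91.0% |

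At alpha 0.05 the requirement is 102, or 105 with equal groups. The value 120 is the smallest balanced N for 90% power at alpha 0.025, which suggests that the two-sided 0.05 was halved. That is an inference; the protocol does not say so.

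The later steps reproduce:

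- Design effect = 1 + (13 − 1) × 0.05 = 1.6.
- 120 × 1.6 = 192, taken up to 15 × 13 = 195.
- 195 / 0.8 = 243.75, rounded up to 244.

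**2. Power with the degrees of freedom the design has.**

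- λ = 195 × 0.4² / 1.6 = 31.2 / 1.6 = 19.5.
- Denominator degrees of freedom = 15 − 5 = 10.
- Power from F(4, 10) = 81.1%. A simulated ANOVA of service means (40,000 runs) gave 81.2%.
- The same λ with F(4, 190) gives 95.5%.
- The f giving 90% power on F(4, 10) is 0.451.

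**3. What would restore 90%.** Suppose the baseline outcome removes a share r² of the variance at both levels (assumption). Then λ = 19.5 / (1 − r²):

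| r | λ | Power, F(4, 10) |
|---|---|---|
| 0 | 19.5 | 81.1% |
| 0.3 | 21.4 | 84.9% |
| 0.4 | 23.2 | 87.8% |
| 0.5 | 26.0 | 91.4% |
| 0.6 | 30.5 | 95.2% |

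The 90% line is crossed at r ≈ 0.46.

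Without adjustment, λ = 31.2 / (1 + 12 × ICC):

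| ICC | Power, F(4, 10) |
|---|---|
| 0.01 | 93.3% |
| 0.02 | 90.5% |
| 0.03 | 87.4% |
| 0.05 | 81.1% |
| 0.10 | 66.2% |

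**4. What would lower it.** Weighting reduces the effective sample by an amount the documents do not give. Purely as an illustration, if each service kept 80%, 70% or 60% of its 13 children in effective terms, unadjusted power would be 75%, 71% or 65%. At 70% with r = 0.5 it would be 84%.

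**5. What f = 0.4 means in SD units.** With five equal groups, the gap between the extreme models is between 2k·f / √(k² − 1) = 4 / √24 = 0.82 SD (models clustered at the two ends) and f·√(2k) = 0.4 × √10 = 1.26 SD (one model at each end, the rest in the middle).

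**The case against.** The strongest reply is that 81% leaves out something the plan includes. Sections 13.1 and 14 both commit to adjusting for the baseline outcome, a correlation near 0.5 would be enough, and the protocol regards 0.05 as a cautious ICC. This stands in part, and it rules out saying that the study fails to deliver 90% power. What remains is that 90% is stated before adjustment, no correlation is given, and 0.05 is the protocol's own planning value. One listed outcome, carer experience of the service, is collected at 12 months only and has no baseline to adjust for. Weighting pulls the other way.

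Two stronger readings are tempting, and the documents support neither.

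- *That the unreproduced 120 is why power falls short.* The direction is wrong: 120 exceeds the 102 to 105 needed at alpha 0.05, so it raises power. Carrying the smaller figure through would shrink the sample. The shortfall comes from the degrees of freedom alone.
- *That 0.4 is a mean difference of 0.4 SD between the extreme models, leaving the study with very little power.* On that reading the unclustered requirement would be about 410 to 970 children, nowhere near 120. The ANOVA wording and the size of N both point to Cohen's f. The metric still needs naming, because section 14 will report adjusted mean differences.

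It is also fair to say that the planned 95% confidence intervals will show how imprecise the comparisons are, and that the sentence on service type changes no computed number.

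**Conclusion.** The concern holds in this form: the stated 90% is not supported by the stated calculation. For 195 analysed children in 15 equal services, ICC 0.05, f = 0.4 and alpha 0.05, unadjusted power is about 81%, some 9 points below the claim; 90% power corresponds to f of about 0.45. Reaching 90% at f = 0.4 requires a baseline correlation of about 0.46 or more, an ICC of about 0.02 or less, or smaller improvements in both, before any loss from weighting or unequal service sizes.

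The result rests on reading 0.4 as Cohen's f and on testing service model against between-service variation, which the planned two-level model implies. The weighting figures are illustrations only. The 120 is a separate matter of an unstated alpha convention and errs on the safe side.

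**What to change.** Revise section 13.1 of the Stage 2 protocol as follows:

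- State power as about 81% unadjusted, from F(4, 10), for 195 analysed children in 15 services at f = 0.4; or equivalently 90% for f = 0.45.
- If 90% at f = 0.4 is to be claimed, give the baseline to 12-month correlation assumed (about 0.46 at ICC 0.05) and its basis, and note that propensity weighting would lower the figure.
- Name the effect size as Cohen's f and give its meaning: 0.82 to 1.26 SD between the extreme models.
- State the alpha used for the F test so that 120 can be reproduced.
- Remove service type from the list of adjustments said to improve power, since it is the exposure.

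Keep N=244 and 15 services. The cost is protocol wording and a less favourable headline figure; no extra children, services or analyses are needed. The Stage 2 SAP should carry the same statement.

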13.2 Missing data

Detail of missing data will be described in the Statistical Analysis Plan (SAP).

13.3 Procedures for reporting deviation(s) from the original Statistical Analysis Plan

Any deviations from the original SAP will be submitted as substantial amendments where applicable and recorded in subsequent versions of the protocol and SAP.

13.4 Inclusion in analysis

All eligible services from Stage 1 of the MELD study will be considered (N=161), and sampling of services will be according to a systematic sampling process. Initially, a stratified sampling approach to selecting services that were included in MELD Stage 1 analyses was proposed. However, a potential complication of this procedure is that services may not continue involvement in Stage 2. Hence, any achieved apparently random sample would be likely be biased.

We propose the following balancing procedure within service models.

1. Rank services based on criteria indicating how likely they conform to a representative example of the service model
2. Secondly rank according to the quality of existing communication between the services and the research team (e.g., it may not be prudent to approach services whose data were obtained in the end with a FOI request).

3. A screening log describing our approach for each service and the outcome of the approach will be recorded. In addition, we will use service-level data as a proxy (that we could obtain for all services) to explore whether we are at risk of selection bias.

14 Analysis

Statistical Analysis

It is inevitable that the referral of children to different service types will be a non-random process. Therefore, a crude comparison of outcomes of children in different service types will be prone to selection bias. To minimise this, the research team and stakeholders will construct a Directed Acyclic Graph (DAG) prior to data collection in Stage 2, which will outline our core assumptions around the causal pathways between service model (exposure) and child outcomes (Williams et al., 2018). This DAG will be used to identify key quantitative data to collect (e.g., confounders, mediators, and moderators) and will be used as an aid for modelling the relationship between service model and child outcomes. The final statistical models will depend on the DAG, but will broadly be a two-level linear regression model (children nested within services), with the child outcome measure at 12-months as the outcome, service model included as a fixed effect, and the corresponding child outcome collected at baseline also included as a covariate. Results will be reported as adjusted mean differences, 95% confidence intervals, and p-values. Mediation analyses will use the bootstrapped procedure as this method has no distributional assumptions on the indirect effect and is generally more robust (Bollen & Stine, 1990).

A detailed statistical analysis plan will be written and agreed by the study management team prior to any analysis taking place. A missing data strategy will be a part of the SAP. This is most likely to include an exploration of any setting/child determinants of missing outcome data (to infer likely missing mechanisms), and an analysis that is valid under a Missing At Random assumption (e.g. using maximum likelihood methods or multiple imputation).

When fitting models to describe the relationship between our service types and our outcome/s, we will adjust for confounding using multinomial propensity score weighting, as this approach tends to preserve the majority of a study sample and therefore maximises precision of estimates. When specifying our propensity score model, we will include outcome risk factors (informed by the DAG which defines the minimally required adjustment set) and exclude strong predictors of service model inclusion that are not associated with outcome. Following this, we will inspect the distribution of

propensity scores for distributional overlap. We will consider trimming of extreme weights (i.e., probabilities close to zero or one), but will investigate the extent to which trimming limits the generalisability of our findings. We will then estimate the “average treatment effect in the whole population” (i.e., the effect of service model on outcomes in all referred children) by fitting models with inverse probability of treatment weights and robust sandwich-type estimators for variance estimation.

Economic Analysis

An economic evaluation of the selected service models will be incorporated into Work Package 2.1; data gathered about co-production activities will be incorporated into Work Package 2.2. This will take the form of a cost-consequence analysis, which will involve the identification, measurement, and valuation of all costs and consequences of the selected service models and co-production activities as well as the presentation of data in a disaggregated tabular format for comparison. The cost consequence analysis will be carried out from a public sector perspective. Data related to the direct costs of each service model will be informed by primary research (using a standard proforma) that will account for the cost of service delivery, monitoring, follow-up, and associated administrative activities. Individual-level data on broader resource consequences and associated economic costs will be informed by CSRs completed by each child’s primary parental caregiver at baseline and at a 12-month follow-up. In addition, data on each measure included in the outcomes package will be collected and reported separately. Mean costs and outcomes for each service model will be estimated together with appropriate measures of uncertainty such as standard errors and confidence intervals. To handle potential selection biases within the economic evaluation, we will apply propensity score matching methods to balance the characteristics of individuals in each comparator group and to ensure consistency with the statistical analysis, before conducting a cost-consequences analysis of the alternative service model types. Our analytical strategy will be informed by recent guidance on the conduct of health economic analyses using individual patient level observational data (Kreif et al., 2013).

A detailed Health Economics Analysis Plan (HEAP) will be written and approved prior to the completion of Stage 2 data collection.

Qualitative Analysis

A Qualitative Analysis Plan will be written for the project and approved prior to data analysis. Data will be organised using NVivo v12. Parkinson et al. (2016) argue that NVivo improves transparency of

the analysis as decisions and interpretations can be traced back to raw data. Data collection, transcription, and analysis will proceed concurrently. This gives the flexibility to explore unanticipated issues with subsequent cases. We will code the data using a Framework approach (Gale et al., 2013; Ritchie & Spencer, 2000; Parkinson et al., 2016). Ritchie and Spencer (2000) argue that framework analysis is useful to describe context, to examine reasons for what exists, to evaluate what is helpful and what can be improved and for identifying new theories, plans or actions.

Framework analysis involves familiarisation; identifying a framework; indexing; charting; and mapping and interpretation. Familiarisation involves really getting to know the data or immersion in the data. This will be achieved by listening to the interviews, reading transcripts, and assigning codes. Discussing issues that arise is an important part of familiarisation. We will discuss with the Study Management Group, including PPI partners. Identifying a framework is a careful balance between issues from the literature, as well as new and emerging issues that come from the data identified in the familiarisation stage. We will be mindful of Stake's (2006) advice to ensure we recognise new issues as they arise. We will do this by keeping careful field notes, by analysing concurrently with data collection, and discussing of expected and unexpected emerging themes within the study team; so both existing and new emerging issues can be accommodated. Indexing applies the framework to each transcript. Charting is really about making the data manageable, summarising, and organising the summaries into charts. Mapping and interpretation involves looking at the key issues in the data, making sense of the data in light of our research questions. We will also carefully consider any data that do not fit in the framework and which suggest rival explanations.

Drawing on Yin (2018) we will also examine, test and refine the following propositions to guide data collection and analysis. These draft propositions have been based on key themes in our qualitative synthesis of existing literature (Griffith & [name], 2014) and individual studies, and will be reviewed by the study team and PPI partners before data analysis commences:

1. Family carers of children with LD and BtC struggle to manage these behaviours, face barriers taking their children into social situations, and can become socially isolated.
2. BtC are functional – serving a purpose/having meaning for the child – and the behaviour/responses of other people is the main mechanism through which BtC are maintained.
3. The quality of the caregiver-professional relationship is central.
4. Some services, or components of services, are effective at providing support for BtC.

5. Organisational barriers can be successfully negotiated in some service models.
6. Co-production of services with family carers and children with LD may enable more appropriate services to be developed.

An important aspect of data analysis will be the cross-case synthesis. In addition to concisely describing each case including its context, we will look across cases to understand the similarities and differences between cases. Our analysis will be informed by Yin's (2018) suggestions of pattern matching, explanation building, and cross case synthesis. This involves looking at the findings in each case, comparing findings across cases, making initial statements, revising the statements in light of the second, third and more cases. We will look for rival explanations in the data (an important part of ensuring rigour) and determine whether these explanations hold up given the actual case study findings. We will refine our propositions. Yin suggests displaying and tabulating data is important, which fits well with our chosen framework analysis approach.

We will ensure there is a clear audit trail that provides a justification of our decisions. Supporting and challenging data will be presented, and in sufficient detail to demonstrate a real understanding of the area.

Integrating qualitative and available quantitative data will be important to enable a more nuanced account of the case study data (Mason et al., 2019). We plan to do this using the techniques proposed by O'Cathain et al. (2010). This will involve both "following a thread" and a "mixed methods matrix" both at the analysis stage. Following a thread was suggested by Moran-Ellis et al. (2006) who proposed an analytical theme or theme in one data set is followed across data sets. They report this as "preserving the value of the open exploratory qualitative inquiry but incorporating the focus and specificity of the quantitative data". The mixed methods matrix is where data are summarised and displayed in a matrix, to look for patterns. This will also fit well with the framework analysis proposed. We plan to use the pillar integration process (Johnson et al., 2019) to display the data. We also note that metaphors for integrated analysis in mixed methods have been proposed by Bazeley and Kemp (2012), and we will draw on these metaphors when discussing integration and interpretation with our stakeholders.

In addition to exploring how services achieve outcomes for children and their families/carers, we will use cross-case comparisons to explore how different service models help or hinder supporting these

processes, how organisational and other barriers are addressed, and how service delivery and acceptability vary according to context.

Talking Mats data

A Talking Mat will be considered completed if children are able to make valid placements of stimuli relevant to the given topic area. A discrete-response coding system will be devised for the current study to verify the validity of children's responses. Researchers will view videos of participants one Talking Mat at a time. Placements will be recorded for each stimulus presented and a confidence rating of high or low will then be made based on an estimation of the validity of the child's response. The observed position of stimuli on a mat following a participant's response will be used to code placements (i.e., the area/column depicting stimuli that is favoured/experienced frequently, or not liked/seldom experienced, or partially liked/experienced). Low confidence ratings will be made if placements appear motivated by acquiescence; are contrary to other communications (e.g., the child says "don't like" and places the item in the highly preferred column); where the child is highly distracted (e.g., placement appears non-intentional), or where placements appear motivated by a sensory stimulation function (e.g., lining items up to create a visually reinforcing display). High confidence will be assumed and rated in the absence of these low confidence indicators.

A second observer will view videos from a randomly selected 50% of participants, in each case coding at least 50% of Talking Mats from the interview and covering all categories of Talking Mat from the study overall. Inter-rater reliability (based on both placements and confidence ratings) will be calculated and reported as a percentage (total agreements divided by total agreements plus total disagreements $\times 100$). In addition, the second observer (a Talking Mats trainer), will complete the Effectiveness Framework of Functional Communication (EFFC) (Murphy and Cameron, 2008) for each mat in their sample. This tool is commonly used in Talking Mats research and provides seven 0–4-point ratings concerning quality of communicative interactions based on the behaviour of both the speaker (child) and listener (researcher). A score of 21 out of 28 represents effective Talking Mats communication.

Researchers will review transcripts in detail and analyse these using a thematic approach (Braun and Clarke, 2022) in relation to each mat, across all children. Transcriptions will be analysed alongside stimuli placement records to support an integration of both data sources and help further explore the manner in which children use the mat and perceive the topic area. Analysis involves comparing what is understood about the child's views, what (and how) views are expressed by the child during

the visit, and how the child is supported to influence interactions and events using whatever skills they have.

Observation data (WP2.2a only)

Observable indicators of the child's engagement, enjoyment, or non-enjoyment will be used to help understand the child's perspectives and experiences.

Observable indicators are observable signs (body language, facial expressions, interactions, speech or vocalisations, behaviours etc.) a person displays that express their feelings. Although there is some similarity between ways people express enjoyment, this this can vary and is unique to each individual, for example some people smile when they are happy whereas other people smile when they are nervous. Asking family carers to identify observable signs of when their child is: enjoying something; not enjoying something; engaged; disengaged; and what is important to or liked by them will reduce subjectivity in the analysis. For each child, family carers will be asked to select up to five key indicators of enjoyment and engagement, and up to five key indicators of non-enjoyment and disengagement.

Observation sheets will be completed to look at what the child appeared to engage with, enjoy, and not enjoy based on these 'observable indicators' in the video recordings. This will be completed by looking at the things that happened before (the "antecedents" to) the child displaying one of their 'observable indicators'.

15 Data Management

Source data will be paper versions of the questionnaires. If physical copies of questionnaires are completed by the Research Assistant face-to face or over the telephone/MS Teams, the Research Assistant will return physical copies of questionnaires to the office as soon as possible, and will store them securely (e.g., in a locked room/cabinet in their home) until this is done. If questionnaires are posted to the participants, they will be returned in free-post envelopes to the MELD Study team. questionnaires will only contain a unique identifier (PID) per participant. No other identifiable information will be recorded on the questionnaires.

Once in the office, physical versions of questionnaires will be stored in locked filing cabinets in lockable offices, and only members of the research team will have access to these data. The Research Assistants

will enter physical versions of questionnaire data on to a secure bespoke database. Once data has been entered and checked for completeness and accuracy by an independent member of the research team (i.e., not the person who entered the data) and upon completion of the study, physical versions of the questionnaires will be destroyed. Online versions of questionnaire data will be stored on Qualtrics and downloaded weekly. The downloads will be securely stored in a study-specific folder on the University of Warwick server, only accessible to research team members. Once data collection has completed for any given part of the study, the data collected online will be transferred to the secure bespoke database with the data entered from physical versions of the questionnaires.

Access to the database will be via username and password and restricted to appropriately trained personnel only. The database will be housed on local servers managed by University of Warwick staff in accordance with all appropriate legislation.

Identifiable data will be password protected and stored separately from non-identifiable data.

Wherever possible data will be validated at point of entry, thereby reducing the opportunity for missing or unexpected data. All changes made to the data will be recorded and visible via an audit log within the database.

Qualitative interviews will be recorded on encrypted audio-recorders or on MS Teams and stored on password protected computers at site. Any transcripts will be fully pseudonymised.

A data management plan will be developed to outline the details of how data will be collected, transferred, stored, and accessed by the team.

The following source data will be collected:

Study data	Source Data					
	Contacts form	Baseline demographic questionnaire	Questionnaires	Written documentation within services	Qualitative interview recordings	Observation recordings
Contacts information	X					
Demographics		X				
Study outcomes			X			
Qualitative interview data (including Talking Mats)					X	
Observations and engagement with children with severe LD						X
Service-level data (including costs)			X			
Review of written documentation for WP2.2a				X		
Review of written documentation for WP2.2b				X		

